### 7.2.2 Procedural data

Procedure data will be displayed separately according to their chronology. Additional procedures will be shown individually including all procedure details, such as for the first documented procedure. The first documented procedure is the basis for main objective calculations (SAP chapter 8.1). Discharge belonging to procedure: Hospital discharge after an additional procedure. For patients with several procedures, there may be several discharge events, too. All events will be processed and analysed, just as the medications associated with the procedure.

### 7.2.3 Follow-up data

Only unique 12MFU form per patient will be used for analysis. If a General Follow-up visit meets the time window of the 12MFU visits (>351d after procedure), manually data review and selection will be performed. Any FU forms older than 440 days after procedure will not be used for analysis (protocol deviation). For patients with contradictory information in the eCRF the following rules are applied:

1. 12 month FU (by phone or visit) is preferred to GFU.
2. Events are always kept, even if GFUs are discarded.

The decision on patient level is given in Appendix F.

12MFU visit and 12MFU by phone results will be analysed combined, where variables were recorded in a similar manner (demographics, symptoms, hospitalization, medication). Not combinable information will be shown separately.

General FU (GFU) data will be assigned to the respective time period after first documented procedure:

- 0 to 3 months (1 day <= time between procedure and GFU <= 90 days)
- 3 to 6 months (90 days < time between procedure and GFU <= 180 days)
- 6 to 9 months (180 days < time between procedure and GFU <= 270 days)
- 9 to 12 months (270 days < time between procedure and GFU <= 351 days)

Multiple GFU per patient within one time period will be shown separately in chronological order (i.e. all first GFUs in one time period, all second GFUs in one time period and so on) as descriptive tables.

Number of GFUs per time period and time (days) until GFU during the time period (for each visit per time period) will be shown. Event rates for clinical events (history of AF, re-ablations and hospitalizations) will be calculated for 3, 6 and 9 months after discharge exactly using appropriate statistical methods.

Predefined time windows for GFU from CIP Version 2.0, Table 7.2 will not be applied.

### 7.2.4 Adverse Event data

Adverse event data (from AE form) will be listed, ordered and reported by seriousness and relatedness to the procedure. Further adverse event analysis are described in the additional objective of this study (SAP chapter 8 and 8.2). For Adverse event analysis only AEAC adjudicated (SUO form) events will be analysed.

## 7.3 Categorisations

Variable categorisations will be done and displayed for all variables created for subgroup definitions (number of patients treated with PVAC GOLD solely). Following variable categorisations will be also displayed:

- Age by categorisation 1 [years]: <65, 65-74, ≥75
- Age by categorisation 2 [years]: <65, 65-75, >75, 75-80, >80
- Weight [kg]: ≤60, >60
- Body Mass Index [kg/m^2]: <18.5, 18.5 to <25, 25 to <30, ≥30 (including WHO obesity classes I-III)
- Number of drinks/day > 10
- HAS-BLED: low, medium, high risk (defined at SAP chapter 7.4.2.1)
- CHA2DS2-VASc: low, medium, high risk (defined at SAP chapter 7.4.2.2)
- Previous ablation (none, 1, ≥ 2)
- Previous surgery for AF (none, 1, ≥ 2)
- Hospitalizations due to AF (none, 1, ≥ 2)
- INR before ablation (INR≤1, 0.85<INR<1.27, INR≥1)

All other categories will be determined based on the distribution of the respective baseline data. Additional categorisations can be added, if necessary.

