Rational: Two known complications that occur during or shortly after the procedure: thromboembolic events including stroke and major bleeding including cardiac tamponade, with an estimated incidence of 1.33% and 0.94%, respectively (23). The combination of heightened risk of both stroke and hemorrhage is linked to the complexity of the AF ablation procedure and the need for adequate peri-procedural anticoagulation. Historically, peri-procedural warfarin therapy was discontinued and replaced with bridging low-molecular-weight heparin (LMWH) before and after the ablation, followed by resumption of warfarin at hospital discharge. Although widely adopted throughout the world and endorsed by current guidelines, it was recognized that this approach may result in a higher incidence of bleeding complications, especially at the site of vascular access (24). Several studies have suggested that continuation of therapeutic warfarin could reduce thromboembolic complications without increasing the risk of hemorrhagic complications (16, 25, 26). However, international normalized ratio (INR) levels often fluctuate during warfarin use, and may not be in the optimal therapeutic range in up to >50% of patients (27). Lower or higher INR levels on the day of ablation may increase the risk of complications. Novel oral anticoagulants (NOACs) are used as an alternative to chronic warfarin for stroke prophylaxis in patients with non-valvular AF. They have fast therapeutic effect without need for INR control and obviating the need for bridging heparin.

The registry will collect data about anticoagulation therapy for Phased RFA and correlate it with the peri-procedural thromboembolic events and bleeding.

Endpoint definition:

- Activated clotting time (ACT) during the procedure
- Peri-procedural INR
- Oral anticoagulant therapy/LMWN before, during and after the procedure
- TIA/stroke related to study Phased RFA procedure

Analysis Methods: Oral anticoagulation medication will be displayed before, after and for each procedure and for the FU. Frequency distributions (counts and percentages) will be presented for each point in time and changes in anticoagulation will be displayed. ACT and peri-procedural INR will be displayed by descriptive statistics (n, mean, SD, median, IQR, minimum and maximum). TIA/stroke event rates related to phased RFA procedure during the first three days after procedure will be calculated using Kaplan Meier estimates.

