# Abbreviations

12MFU	12 months follow-up
ACE inhibitors	Angiotensin-Converting
ACT	Activated Clotting Time
AE	Adverse Event
AF	Atrial Fibrillation
AFEQT	Atrial Fibrillation Effect on Quality of Life (Questionnaire)
Afl	Atrial Flutter
ASA	AcetylSalicylic Acid
AT II antagonist	Angiotensin Receptor II Antagonist
AV-Block	AtrioVentricular Block
CABG	Coronary Artery Bypass Graft
CFAE	Complex Fractionated Atrial Electrograms
cGy	CentiGray
CHA2DS2-VASc	Score for Stroke Risk Components: cardiac failure, hypertension, age $\geq 75$ (doubled), diabetes, stroke (doubled)-vascular disease, age 65–74 and sex category (female)
CI	Confidence Interval
CIP	Clinical Investigational Plan
cm	Centimeter
COPD	Chronic Obstructive Pulmonary Disease
CRF	Case Report Form
CRO	Contract Research Organisation
CRT	Cardiac Resynchronization Therapy
CT	Computed Tomography
CV	Cardio Version
CVD	Cardiovascular Disease
DAP	Dose Area Product
dd.mm.yyyy	Date with Day.Months.Year
EBogen	Electronic Data Capture System of the Institut für Herzinfarktforschung
ECG	Electrocardiogram
eCRF	Electronic Case Report Form
EDC	Electronic Data Capture
EGM	Electrogram
EHRA	European Heart Rhythm Association
EP	Electrophysiology
FU/GFU	Follow-up/General Follow-up
GmbH	Gesellschaft mit beschränkter Haftung (limited liability company)
HAS-BLED	Score for Major Bleeding Risk Components: hypertension, abnormal renal/liver function (1 point each), stroke, bleeding history or predisposition, labile INR, elderly ( $>65$ ), Drugs/alcohol concomitantly (1 point each)
HF	Heart Failure
hh:mm	Time with Hours.Minutes
ICD	Implantable Cardioverter-Defibrillator
ICM	Implantable Cardio Monitor
IHF	IHF GmbH - Institut für Herzinfarktforschung, Ludwigshafen

ILR	Implantable Loop Recorder
INR	International Normalized Ratio
IPG	Implantable Pulse Generator
IVC	Inferior Vena Cava
kg	Kilogram
LA	Left Atrium
LAAO	Left Atrial Appendage Occluder
LCPV	Left Common Pulmonary Vein
LIPV	Left Inferior Pulmonary Vein
LMWH	Low-Molecular-Weight Heparin
LSPV	Left Superior Pulmonary Vein
LV	Left Ventricle
LVEF	Left Ventricular Ejection Fraction
MAAC	Multi-Array Ablation Catheter
MASC	Multi-Array Septal Catheter
MDT	Medtronic
mGy*cm 	MilliGray Square Centimeters
MI	Myocardial Infarction
min	Minute
ml	Milliliter
mm	Millimeters
mmHg	Millimeters of Mercury
MRI	Magnet Resonance Imaging
NA	Not Applicable
NIS	Non-interventional Study
no.	Number
NOAC	Novel Oral Anticoagulant
NSAID	NonSteroidal Anti-Inflammatory Drugs
NSR	Normal Sinus Rhythm

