#### 7.4.2.2 CHA2DS2-VASc Score

The CHA2DS2-VASc Score is based on eight variables which contribute (if fulfilled) to the score by each point:

Risk Factor / Variable	Points
Congestive heart failure/LV dysfunction*	1
Hypertension**	1
Age > 75	2
Diabetes Mellitus	1
Stroke or TIA or thromboembolic event	2
Vascular disease (prior myocardial infarction, peripheral artery disease, or complex aortic plaque)	1
Age 65 – 74 y	1
Sex category (female gender)	1

\* Congestive heart failure / LV dysfunction is defined as present, if chronic heart failure is ticked "yes"

\*\* Hypertension is defined as present, if hypertension is ticked "yes"

If one of the variables that is contributing to the CHA2DS2-VASc Score is missing, the score is not calculated.

The maximum of the CHA2DS2-VASc Score is 9 points. A categorisation into low / medium / high risk is given by:

Range	Risk
0	low
1	medium
2 or more	high

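### The SAP's CHA2DS2-VASc table gives a 75-year-old no age points, and its INR classes and second age grouping overlap; only the categorised displays are affected

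*SAP*

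**What the plan says.** **INR classes.** SAP 7.3 lists "INR before ablation (INR≤1, 0.85<INR<1.27, INR≥1" among the categorisations to be displayed. It does not say that the classes are meant to overlap.

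**Age groupings.** The same list has two. The first is "Age by categorisation 1 [years]: <65, 65-74, ≥75", which Appendix D also uses for its age comparison. The second is "Age by categorisation 2 [years]: <65, 65-75, >75, 75-80, >80".

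**Stroke-risk score.** SAP 7.3 also displays "CHA2DS2-VASc: low, medium, high risk (defined at SAP chapter 7.4.2.2"). The point table in SAP 7.4.2.2 gives 2 points for age > 75 and 1 point for age 65 to 74. The same section puts 0 points in the low class, 1 in the medium class and 2 or more in the high class. The SAP abbreviation list defines the score differently: "Score for Stroke Risk Components: cardiac failure, hypertension, age $\geq 75$ (doubled").

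**The concern.** A categorisation should place each patient in exactly one class, and a score should give each patient one unambiguous value. Three items in the SAP fail this test.

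- The INR classes are not mutually exclusive. A table built to the letter counts some patients two or three times. A programmer who tests the conditions in sequence gets counts that depend on the order of testing, so the table cannot be reproduced from the SAP.
- The age rule in the score leaves a hole at 75. Some patients of that age would be shown in a lower stroke-risk class than the SAP's own definition gives them.
- The second age grouping is ambiguous at 75.

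At stake is the description of who was ablated, by stroke risk, by INR and by age. Baseline and first-procedure tables are planned for the interim as well as the final analysis (SAP Appendix B), and interim results may be published (SAP 8.4).

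**Working it through.** **1. Reproduce the plan's own figure.** SAP 7.4.2.2 states a maximum score of 9. The two age items exclude each other, so the maximum is heart failure 1 + hypertension 1 + age > 75 2 + diabetes 1 + stroke 2 + vascular disease 1 + female sex 1 = 9. This agrees, so the point table has been read as intended.

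**2. Age points by age in whole years.**

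| Age | Point table, SAP 7.4.2.2 | Abbreviation list (≥ 75 doubled) |
|---|---|---|
| 64 | 0 | 0 |
| 65 | 1 | 1 |
| 74 | 1 | 1 |
| 75 | 0 | 2 |
| 76 | 2 | 2 |

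Under the point table, a patient of 75 scores less for age than one of 74 or 76. If ages were kept with decimals, every value above 74 up to and including 75 would score nothing.

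**3. Effect on the risk class at age 75.** Let *o* be the points from the other six factors. The point table gives *o* + 0, and the abbreviation list gives *o* + 2.

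- *o* = 0: 0 (low) against 2 (high).
- *o* = 1: 1 (medium) against 3 (high).
- *o* ≥ 2: high under both, so only the score differs.

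Six yes/no factors give 2^6 = 64 combinations. One has *o* = 0. Five have *o* = 1 (heart failure, hypertension, diabetes, vascular disease or female sex alone; stroke carries 2 points). The class therefore changes in 1 + 5 = 6 of 64 combinations. These are combinations of factors, not patient frequencies.

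**4. INR class membership.** The plausibility range in SAP Table 3 is 0.5 to 9.

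| INR | ≤ 1 | 0.85 to 1.27 | ≥ 1 | Classes |
|---|---|---|---|---|
| up to 0.85 | yes | no | no | 1 |
| above 0.85, below 1 | yes | yes | no | 2 |
| exactly 1 | yes | yes | yes | 3 |
| above 1, below 1.27 | no | yes | yes | 2 |
| 1.27 and above | no | no | yes | 1 |

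At one decimal place, 0.9, 1.1 and 1.2 are counted twice and 1.0 three times.

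Let *f* be the share of patients with INR above 0.85 and below 1.27, and *g* the share at exactly 1.0 (included in *f*). The class percentages then add to 100 × (1 + *f* + *g*). The documents give neither share. As an illustration only, assuming *f* between 0.30 and 0.60, the sum is at least 100 × 1.30 = 130% to 100 × 1.60 = 160%.

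**5. Second age grouping.** Age 75 is in both 65-75 and 75-80. Ages 76 to 80 are in both > 75 and 75-80. Ages over 80 are in both > 75 and > 80.

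**The case against.** The strongest case on the other side is that little depends on these items, and most of that case stands.

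- A reader might infer that the anticoagulation tables are wrong. The documents do not support this. CHA2DS2-VASc appears neither in SAP 8.3.3 nor in SAP Table 11. Protocol 4.4.3 summarises INR there as a continuous variable, and Table 11 takes the measured value and its date. ACT, medication and TIA/stroke outputs do not use the classes.
- The protocol remark "Lower or higher INR levels on the day of ablation may increase the risk of complications" might suggest a planned comparison of INR classes. It is background rationale. The planned correlations in SAP Table 13 mention no classes.
- A reader might also infer that an anticoagulated patient cannot be told apart from one with INR 1.0, because both meet the condition ≥ 1. But 1.0 falls in all three classes, while 1.27 and above falls only in the third. The INR value and the medication are also recorded, and Appendix C separates continued from discontinued oral anticoagulation.
- Neither the INR classes nor the stroke-risk class defines a predefined subgroup, comparison group or graph. The Appendix D age comparison uses the first, sound grouping.
- In the second age grouping, > 75 may be a subtotal of the two groups after it. That explains the nesting, but not age 75, which sits in 75-80 without being > 75 and also sits in 65-75.

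The objection does not remove the contradiction between the point table and the abbreviation list, or the overlap of the INR classes. A lost symbol in the PDF is an unlikely explanation, since the ≥ sign survives in the neighbouring HAS-BLED section.

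**Conclusion.** The faults are certain and their reach is small. Followed literally, the SAP scores every 75-year-old 2 points below its own abbreviation-list definition. It shows the wrong risk class for those with no other factor or exactly one 1-point factor. INR values between 0.85 and 1.27 are counted twice, or three times at exactly 1.0, and age 75 is counted twice in the second age grouping. The effect stops at the categorised displays of baseline risk, INR and age.

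This rests on age being held in completed years and on the rules being programmed as written. How many patients are affected cannot be computed from the documents. If 2% to 4% of 800 to 1000 patients were aged 75 (an assumption), 0.02 × 800 = 16 to 0.04 × 1000 = 40 would carry a wrong score. Only those among them with no other factor or a single 1-point factor would change class.

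**What to change.** - **SAP 7.4.2.2:** change age > 75 to age ≥ 75, to agree with the abbreviation list, the first age grouping and Appendix D. State that age is in completed years. The maximum score stays at 9.
- **SAP 7.3, INR:** make the classes mutually exclusive. The SAP's own limits would give ≤ 0.85, > 0.85 to < 1.27, and ≥ 1.27, but the sponsor should confirm the intended cut-points. The documents give no numerical therapeutic range, so they offer no basis for splitting the top class further.
- **SAP 7.3, second age grouping:** restate it as < 65, 65-74, 75-80, > 80. Alternatively, keep the older group as a labelled subtotal with the boundary at 75 corrected.

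The cost is SAP wording and a few lines of code. No new data are needed.

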## 7.4 Transformation of Data

### 7.4.1 (Re-)Calculation of derived variables

Body Mass Index [kg/m^2]

ROUND (body weight [kg] / (body height [cm] / 100) ^2), .01)

Time to event

For the time to event analysis, the time until the occurrence of an event is presented in days [d] and calculated as follows:

Date of event occurrence – date of first documented procedure

Length of stay in rehabilitation [days]

ROUND((Date of discharge - Date of referral),1)

DAPT [dichotomous]

Dual antiplatelet therapy: Combination of Aspirin and an P2Y12 inhibitor (Clopidogrel, Prasugrel or Ticagrelor).

#### Procedure Timing

- General time of the procedure = defined and calculated by eCRF
- Time in between vessel access = time of last catheter removal – first vessel access
- Lab occupancy time = Time patient left the Catheter Lab - Time patient delivered to the Catheter Lab
- PVAC ablation time = Time of last PVAC ablation - Time of first PVAC ablation
- MAAC duration = Time of last MAAC ablation - Time of first MAAC ablation
- MASC duration = Time of last MASC ablation - Time of first MASC ablation

## 7.4.2 Risk scores

### 7.4.2.1 HAS-BLED Score

The HAS-BLED Score is based on nine variables which contribute (if fulfilled) to the score by each point:

Risk Factor / Variable	Points
Hypertension*	1
Abnormal	
renal function	1
liver function	1
Stroke/TIA	1
Bleeding	1
Labile INR	1
Elderly (> 65)	1
Drugs (antiplatelets or NSAID)	1
alcohol abuse**	1

\* Hypertension is defined as present, if hypertension is ticked "yes" and/or the systolic BP is  $\geq 160$ mmHg

\*\* Alcohol abuse is defined as  $\geq 2$  drinks per day

If one of the variables that is contributing to the HAS-BLED Score is missing, the score is not calculated.

The maximum of the HAS-BLED Score is 9 points. A categorisation into low / medium / high risk is given by:

Range	Risk
0 or 1	low
2	medium
3 or more	high

#### 7.4.2.2 CHA2DS2-VASc Score

The CHA2DS2-VASc Score is based on eight variables which contribute (if fulfilled) to the score by each point:

Risk Factor / Variable	Points
Congestive heart failure/LV dysfunction*	1
Hypertension**	1
Age > 75	2
Diabetes Mellitus	1
Stroke or TIA or thromboembolic event	2
Vascular disease (prior myocardial infarction, peripheral artery disease, or complex aortic plaque)	1
Age 65 – 74 y	1
Sex category (female gender)	1

\* Congestive heart failure / LV dysfunction is defined as present, if chronic heart failure is ticked "yes"

\*\* Hypertension is defined as present, if hypertension is ticked "yes"

If one of the variables that is contributing to the CHA2DS2-VASc Score is missing, the score is not calculated.

The maximum of the CHA2DS2-VASc Score is 9 points. A categorisation into low / medium / high risk is given by:

Range	Risk
0	low
1	medium
2 or more	high

#### 7.4.3 Scoring of questionnaire data (AFEQT)

##### Symptom subscale score

In a first step, the levels of the 7 answer categories (equal to the order of appearance) for the 4 questions contributing to the Symptom subscale (i.e. questions 1, 2, 3, 4) are coded as follows:

level 1 ( not at all bothered ) OR I did not have this symptom)	→ 1
level 2 ( hardly bothered )	→ 2
level 3 ( a little bothered )	→ 3
level 4 ( moderately bothered )	→ 4
level 5 ( quite a bit bothered )	→ 5
level 6 ( very bothered )	→ 6
level 7 ( extremely bothered )	→ 7

In a second step, using the assigned values the Symptom subscale is calculated as follows:

$$100 - \left[ \frac{(\text{sum of severity for questions 1, 2, 3, and 4 answered} - \text{number of questions answered}) \times 100}{(\text{total number questions answered} \times 6)} \right]$$

### Daily Activities subscale score

In a first step, the levels of the 7 answer categories (equal to the order of appearance) for the 8 questions contributing to the Daily Activities subscale (i.e. questions 5, 6, 7, 8, 9, 10, 11, 12) are coded as follows:

#### **(a) Questions 5 and 6:**

level 1 ( not at all limited )	→ 1
level 2 ( hardly limited )	→ 2
level 3 ( a little limited )	→ 3
level 4 ( moderately limited )	→ 4
level 5 ( quite a bit limited )	→ 5
level 6 ( very limited )	→ 6
level 7 ( extremely limited )	→ 7

#### **(b) Questions 7 to 12:**

level 1 ( no difficulty at all )	→ 1
level 2 ( hardly any difficulty )	→ 2
level 3 ( a little difficulty )	→ 3
level 4 ( moderate difficulty )	→ 4

level 5 ( quite a bit of difficulty )	→ 5
level 6 ( a lot of difficulty )	→ 6
level 7 ( extreme difficulty )	→ 7

In a second step, using the assigned values the Daily Activities subscale is calculated as follows:

$$100 - \left[ \frac{(\text{sum of severity for questions 5, 6, 7, 8, 9, 10, 11, and 12 answered} - \text{number of questions answered}) \times 100}{(\text{total number questions answered} \times 6)} \right]$$

#### Treatment Concern subscale score

In a first step, the levels of the 7 answer categories (equal to the order of appearance) for the 6 questions contributing to the Symptom subscale (i.e. questions 13, 14, 15, 16, 17, 18) are coded as follows:

level 1 ( not at all bothered )	→ 1
level 2 ( hardly bothered )	→ 2
level 3 ( a little bothered )	→ 3
level 4 ( moderately bothered )	→ 4
level 5 ( quite a bit bothered )	→ 5
level 6 ( very bothered )	→ 6
level 7 ( extremely bothered )	→ 7

In a second step, using the assigned values the Treatment Concern subscale is calculated as follows:

$$100 - \left[ \frac{(\text{sum of severity for questions 13, 14, 15, 16, 17, and 18 answered} - \text{number of questions answered}) \times 100}{(\text{total number questions answered} \times 6)} \right]$$

#### Treatment Satisfaction subscale score

In a first step, the levels of the 7 answer categories (equal to the order of appearance) for the 2 questions contributing to the Symptom subscale (i.e. questions 19, 20) are coded as follows:

level 1 ( extremely satisfied )	→ 1
level 2 ( very satisfied )	→ 2
level 3 ( somewhat satisfied )	→ 3
level 4 ( mixed with satisfied and dissatisfied )	→ 4

level 5 ( somewhat dissatisfied )	→ 5
level 6 ( very dissatisfied )	→ 6
level 7 ( extremely dissatisfied )	→ 7

In a second step, using the assigned values the Treatment Satisfaction subscale is calculated as follows:

$$100 - \left[ \frac{(\text{sum of severity for questions 19 and 20 answered} - \text{number of questions answered}) \times 100}{(\text{total number questions answered} \times 6)} \right]$$

### Overall AFEQT score

In a first step, the levels of the 7 answer categories (equal to the order of appearance) for the 20 questions contributing to the Symptom subscale (i.e. questions 1 to 20) are coded as follows:

